their local IRB, if there is one, for institutional review. Institutional review of each site's local requirements (e.g., human subject training requirements, conflict of interest, and consent forms to ensure locally required language is included for compensation for injury, conflict of interest, etc.) and "non-IRB" institutional reviews by ancillary committees (e.g., institutional biosafety, radiation safety) must be performed by each institution, as applicable.

The BMC team will not obtain verbal consent from participants to share their contact information with the study team. Instead, the BMC team will distribute IRB approved flyers throughout the center, and participants will be given the option to self-refer. BMC will also provide study team members who will act as group leaders for the M-ROCC arm of the study. Context surrounding adverse events will be shared with the relevant BMC team members, as is outlined in protocol section 7.5.

### **3. PRÉCIS**

#### **Study Title**

Effect of Mindfulness Training on Opioid Use and Anxiety During Primary Care

Buprenorphine Treatment

#### **Objectives**

We will conduct a randomized controlled trial comparing a live-online Mindful Recovery Opioid Care Continuum (M-ROCC) group (a motivationally-responsive, trauma-informed extended 24-week Mindfulness-Based Intervention (MBI) with an ascending practice dose ladder approach that offers mindfulness training instruction optimized to enhance self-regulation and catalyze recovery) with a live-online control group, to examine the efficacy of M-ROCC on abstinence from illicit opioids while also targeting co-morbid anxiety, pain, and substance use (cocaine, benzodiazepines (BZD)).

#### **Design and Outcomes**

This will be a RCT designed to compare live-online M-ROCC groups with a live-online control group on the primary outcome of the number of biochemically confirmed illicit opioid negative abstinent periods (defined by a negative oral fluid test [negative for opiate, oxycodone, fentanyl, methadone] AND no self-reported illicit opioid use) during weeks 13-24 of study (six two-week periods of opioid abstinence during the final 12 weeks of the study).

Clinical secondary outcomes include level of anxiety measured by the Patient Reported Outcomes Measurement Information System – Anxiety Short Form 8a (PROMIS-ASF), level of pain interference measured by the PROMIS Pain Interference Scale (PROMIS-PISF), and the number of positive oral fluid tests for BZD or cocaine during the final 12 weeks of the study. Other exploratory outcomes will be level of anxiety measured by the Beck anxiety inventory (BAI), 24-week intervention retention, as well as mechanisms of self-regulation assessed by self-report and behavioral measures (emotion regulation, decentering/metacognitive monitoring, interoception, experiential avoidance, self-critical rumination, and self-compassion) and their mediating effects on anxiety and opioid abstinence. Qualitative interviews will be conducted with a minimum of 12 and a maximum of 30 M-ROCC or control group completers until thematic saturation to examine themes regarding live-online mindfulness delivery and to compare responses with our R21 qualitative outcomes from our in-person M-ROCC group model. Computerized Adaptive Testing for Mental Health (CAT-MH) will be used to assess changes in psychiatric co-morbidity. Finally, exploratory outcomes of stigma, mindfulness, perceived stress, pain catastrophizing, interpersonal conflict, and shared identity within group will be measured.

## **Interventions and Duration**

### Live-Online M-ROCC:

The live-online M-ROCC program is directly adapted from Mindfulness Training for Primary Care (MTPC), which was developed and tested in the MINDFUL-PC research study and piloted for OUD in the R21 study. M-ROCC is based on a model of human experience which identifies experiential avoidance and disconnection from our bodies and from others as fundamental causes of human distress, and addictive behavior in particular. M-ROCC is a 6-month long Mindful Recovery OUD Care Continuum designed with the clinical needs of OUD participants to be delivered in primary care clinics. Due to COVID-19, this study will test the curriculum delivered in a virtual setting online as a research intervention separate from clinical care. Below we describe the adjustment of the program with logistical constraints of the COVID-19 pandemic in mind. The M-ROCC curriculum focuses on integration of mindfulness practice for living well through stress, anxiety, depression, pain and addiction recovery. The M-ROCC curriculum has three primary components.

- 1) LDM (Low-Dose Mindfulness): A four-week introductory mindfulness program for OUD with monthly rolling admission, which includes 50 minutes of mindfulness introduction and explicit training in the use of mobile mindfulness

apps. LDM introduces participants to the ascending practice dose ladder. The live online session will be 80-90 minutes with 30 minutes of group check-in and online toxicology testing with staff followed by 60 minutes of the mindfulness program.

- 2) MTPC-ODU (Mindfulness Training for Primary Care – OUD): A sixteen-hour curriculum delivered in either (a) eight-week intensive mindfulness group with an ascending practice dose ladder and skill integration over the course of the eight weeks, 120 minutes per session, or (b) sixteen-week intensive mindfulness group with an ascending practice dose ladder and skill integration over the course of sixteen weeks with 60 minutes per session. While the LDM group format will be delivered in the same manner in all study cohorts, the MTPC-ODU curriculum format will be interchangeable in different cohorts depending on the implementation needs of group leaders. The live online session will be 80-90 minutes with 30 minutes of group check-in and online toxicology testing with staff followed by 60 minutes of the mindfulness program.
- 3) MCS (Mindfulness Maintenance Check-in Support): Various ongoing weekly mindfulness continuation groups with check-in and reminders, leveraging mobile mindfulness application and motivational-oriented counseling for graduates of LDM for 50 minutes of mindfulness practice. MCS will be available for the duration of the study. After LDM completion, 20 weeks is the longest expected duration of MCS for a participant who goes directly from LDM to MCS and does not choose to enroll in MTPC-ODU. Free MCS groups will be available through the CMC Free Live Online Community Program.

Within the M-ROCC curriculum there is flexibility, so that each participant who enrolls will begin in LDM for four weeks. If the participant is able to develop a home practice and begins ascending the practice ladder, then they will be given the option to move to the intensive MTPC-ODU or the ongoing MCS depending on readiness. Participants can repeat LDM, transfer to the MCS group or transition from the LDM or MCS into intensive MTPC, forming a continuous practice and check-in support continuum that encourages increased practice with the spirit of autonomy, collaboration, and naturalistic selection based on participant motivation and capacity.

#### Live-Online Control Group:

The live-online control group will be attention- and time-matched to the M-ROCC LDM and MCS groups. This weekly control group will run for 80-90 minutes, with 30 minutes of group check-in and online toxicology testing with staff followed by 50-60 minutes of group time. As an active group comparator, this group will isolate

mindfulness components by controlling for the therapeutic aspects of a group. Group content is derived from commonly used methods in community substance use disorder treatment and recovery groups, including elements of Motivational Interviewing, CBT, Community Reinforcement, and Twelve Step Facilitation, as well as educational and didactic components. These live-online control groups will function as research groups only and will not replace standard of care at sites, but they may provide a therapeutic benefit to participants lacking a recovery group due to the constraints of COVID-19.

### **Sample Size and Population**

We anticipate an approximate enrollment of N=236 with a maximum of N=280 participants prescribed buprenorphine from Connecticut, Florida, Maine, Massachusetts, New Hampshire, New York, Rhode Island, Texas, Vermont, California, North Carolina, Virginia, Alabama, Arizona, Illinois, or Michigan over eight months. We anticipate enrolling approximately 30 participants per month. We anticipate 192 (81%) participants to be randomized (1:1 ratio, block size of 4, 6, 8 to M-ROCC or live-online control, respectively) in online groups (n=96 M-ROCC, n=96 Control), and of these we anticipate 45 (47% of those who began LDM) will begin the 16 session MTPC-ODU intensive group. This estimate is based on our experience in the R21 Mindful-OBOT pilot, in which 47% of participants enrolled in our initial pilot site began an MTPC-ODU group.

Participants will be patients living in U.S. states approved by the IRB for recruitment who are prescribed Buprenorphine. We will recruit from one of the three non-CHA affiliated sites from collaborating institutions that offer primary care office-based opioid treatment, from two sites affiliated with CHA, and from OBAT sites in U.S. states approved by the IRB for recruitment, and also via Facebook and Instagram. Participants must be 18-70 years old and must be able to use an electronic device with a video camera to attend study groups and complete questionnaires. This study will enroll individuals of any gender, and any demographic group, including pregnant women.

Participants must have a diagnosis of opioid use disorder, be prescribed buprenorphine, have sufficient English fluency to understand procedures and questionnaires, and be without acute severe mental illness (mania, psychosis, suicidality with intent/plan) and ability to provide informed consent. This trial is limited to English-speaking participants at this time since the intervention curricula have not been adapted to other languages.

## 1. STUDY OBJECTIVES

### 1.1 Primary Objective

**1.1.a. Opioid Abstinence:** Compare effects of live-online M-ROCC vs. a live-online control group on the number of biochemically confirmed illicit opioid negative abstinent periods (defined by negative oral fluid tests [negative for opiate, oxycodone, fentanyl, methadone] AND no self-reported illicit opioid use) during weeks 13-24 of study.

**H1a:** M-ROCC will have more abstinent time periods than the control group during weeks 13-24.

### 1.2 Secondary Objectives

**1.2.a. Clinical Co-morbidity:** Compare effects of M-ROCC vs. the control arm on anxiety and pain.

**H2a:** Among those with anxiety disorders, M-ROCC will have greater reduction in anxiety than control group at 24 weeks.

**H2b:** M-ROCC will have greater reduction in pain interference than control group at 24 weeks.

**1.2.b. Cocaine and Benzodiazepine Use:** Compare effects of live-online M-ROCC vs. the control arm on cocaine and benzodiazepine use.

**H3a:** M-ROCC will have fewer positive oral fluid tests for cocaine than a control group during weeks 13-24.

**H3b:** M-ROCC will have fewer positive oral fluid tests for BZDs than a control group during weeks 13-24.

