The COVID-19 pandemic also threatens Office-Based Opioid Treatment (OBOT) by restricting access to in-person treatment for co-morbidity that can impact BUP treatment outcomes. The pandemic has led to nationwide changes in OUD treatment. Many primary care facilities are presently unable to hold in-person Group Based Opioid Treatment (GBOT) groups. Therefore, it is crucial that these services be delivered in a feasible online format such that OUD patients can still receive the quality care they need.

More than 30% of patients with OUD get benzodiazepine (BZD) prescriptions during the first year of opioid treatment. Early in treatment, patients receiving B/N treatment frequently request a benzodiazepine prescription to mitigate anxiety and insomnia symptoms, to deal with psychosocial stress, and to regulate emotions. Among those in

OBOT who do not receive a BZD prescription, 67% still report a history of BZD misuse. Mixing BZDs and opioids can lead to synergistic overdose, cognitive impairment, and accidental injuries. Heavy BZD use reduced HCV antiviral treatment uptake. Much concern and debate exists about BZD diversion within B/N programs. Therefore, non-pharmacologic approaches to anxiety, stress, and emotional dysregulation are needed.

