Based on R21 urine toxicology data, we will focus our primary outcome analysis on the impact of M-ROCC on opioid use starting 12 weeks after intervention assignment. We estimate a mean of 4.67 negative tests for all illicit opioids (opiates, oxycodone, fentanyl, methadone) out of 6 random oral fluid toxicology tests conducted during the last 12 weeks in M-ROCC (SD 1.23) ( $n=78$ ) and 4.11 negative tests for all illicit opioids in the control check-in group (SD 1.27) ( $n=78$ ). We anticipate an effect size of Cohen's  $d = 0.45$  for between-group difference in percentage of monthly positive toxicology screens. Participation of  $N=192$  individuals randomized (with an effective sample size of 156 with 78 individuals in the M-ROCC arm and 78 individuals in the control group) allows for  $> 80\%$  power to detect an effect size of 0.45 for negative toxicology for all illicit opioids between M-ROCC and control arms. This power calculation was generated assuming a t-test of the difference between two means, a 1:1 intervention to control recruitment ratio, a type I error of 0.05, a two-sided comparison, and a design effect of 1.23 derived from an ICC of 0.01 with 8 group clusters with average cluster size of 24, which represents the average number of people randomized in each monthly cohort to either live-online M-ROCC or the live-online control group. This level of cluster was selected because it will encompass cohort effects. As the primary outcome will be analyzed in an intent-to-treat analysis, it is not sensitive to the number of individuals who drop out of the study after randomization. For secondary outcomes, based on pilot data and other relevant studies, we anticipate dropout from intervention in M-ROCC between 17-28% at 24-weeks and dropout in the control groups of 21-44% at 24-weeks.

In previous primary care studies, we have reported the impact of MTPC over 24 weeks on reductions in anxiety as measured by the PROMIS-ASF as  $d = -0.72$  ( $n=81$ ),  $p<0.001$  and  $d = -0.80$ ,  $p<0.001$  ( $n=136$ ). In our recent R21 pilot study, we reported significant Anxiety reductions over 24 weeks among patients with co-morbid anxiety at baseline ( $\geq 55$  at baseline) ( $p < .05$ ,  $ES = -0.556$ ). Given the

likelihood of a small effect of control on Anxiety after 4 weeks of buprenorphine treatment, we anticipate an effect size of  $d = -0.56$  for between-group change in PROMIS-ASF.

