### 9.5.2 Secondary Outcomes

#### Main Secondary Clinical Outcomes:

1. Patient Report Outcomes Measurement Information System – Anxiety Short Form 8a (PROMIS-ASF)
2. Patient Report Outcomes Measurement Information System – Pain Interference Scale (PROMIS-PISF)
3. Positive oral fluid toxicology tests for Cocaine during the final 12 weeks (weeks 13-24) of the study.
4. Positive oral fluid toxicology tests for Benzodiazepines during the final 12 weeks (weeks 13-24) of the study.

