**Weekly Survey:** Participants will receive a weekly password protected REDCap survey gathering information about their substance use in the last week, retention, buprenorphine adherence, their level of care (e.g., at a detox residential place, regular outpatient, primary care, etc.), enrollment in medication-assisted treatment, as well as their Buprenorphine and Benzodiazepine (if applicable) dosages. This

survey will be sent via an email link to the secure, encrypted REDCap database. If this is impossible this information will be collected using a CHA-IT approved device. Duration: 4 min

**Pain Catastrophizing Scale (PCS):** The Pain Catastrophizing Scale (PCS) is a 13-item scale designed to facilitate research on the mechanisms by which catastrophizing impacts pain experience. Participants will be asked to indicate the degree to which they experience certain thoughts and feelings when experiencing pain (e.g. “I feel I can’t go on”) on a scale from 0 (“Not at all”) to 4 (“All the time”). Duration: 3 min.

**Substance Craving Scale (SUBCS):** The Substance Craving Scale (SUBCS) is a 6-item scale adapted from the Opioid Craving Scale (OCS). The SUBCS assesses participant craving for Opioids (including fentanyl, heroin, methadone, oxycodone or other opioids) and other substance use (including illicit drugs [e.g., cocaine, methamphetamine, etc.], using unprescribed pills [e.g., Adderall, etc.], using prescribed medication in ways or at doses for which they were not prescribed [e.g., Klonopin, etc.], or drinking alcohol). Duration: 2 min.

*Self-Regulation Battery:*

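### H3b counts every benzodiazepine-positive test, and section 9.6 attaches no baseline adjustment to it, so precision is lost that the pre-randomization test could partly recover

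*Combined protocol and SAP*

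**What the plan says.** **Outcome.** H3b (section 1.2) predicts that "M-ROCC will have fewer positive oral fluid tests for BZDs than a control group during weeks 13-24". Item 4 of the main secondary outcomes in 9.5.2 is "Positive oral fluid toxicology tests for Benzodiazepines during the final 12 weeks (weeks 13-24) of the study". Neither separates positives explained by a prescription from other positives.

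**Who can enroll.** The abstinence criterion in 4.1 concerns non-prescribed use. No exclusion in 4.2 names a BZD prescription. The plan expects prescribed users: the weekly survey in 10.1 asks about substance use "as well as their Buprenorphine and Benzodiazepine (if applicable) dosages", and prescribed BZD dose is a separate exploratory clinical outcome in 9.5.2.

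**Baseline data.** Table 1a marks oral fluid toxicology in the Baseline column, and the screening text in 6.2.2 describes a supervised test before eligibility is settled. Both precede randomization. The BZD dosage item belongs to the weekly survey, which starts in week 1.

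**Analysis.** Section 9.6 lists the BZD count among the secondary outcomes without a model or covariates. The primary-outcome GEE is to be fitted with covariates that are not listed. The covariate list later in 9.6 belongs to the retention analysis, applies in case of chance imbalance, and includes baseline cocaine use but not baseline BZD use. Section 4.3 adds scheduling acceptability as a covariate in general.

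**The concern.** A person who uses a BZD steadily, prescribed or not, will tend to be positive at most of the six tests, while most other participants score near zero. The count is then a mixture of two distant groups, and its variance is dominated by which group a person belongs to. That membership is largely visible in the test taken before randomization. If the model ignores it, the variance stays in the residual.

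A null result on H3b could then reflect noise from persistent users rather than an absence of effect, and a reader could not tell which. A rule that adds a covariate only after a significant imbalance does not help, because the gain from a strong prognostic covariate does not depend on imbalance.

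**Working it through.** **1. The plan's own figure.** Section 9.2 powers only the primary outcome, using "a type I error of 0.05, a two-sided comparison, and a design effect of 1.23 derived from an ICC of 0.01" and "8 group clusters with average cluster size of 24".
- Design effect = 1 + (24 − 1) × 0.01 = 1.23.
- 192 / 1.23 = 156.1, the stated "effective sample size of 156 with 78 individuals in the M-ROCC arm and 78 individuals in the control group".
- Power at d = 0.45, two-sided 0.05, 78 per arm: 0.802 (normal approximation), 0.797 (t). This agrees with the plan's figure of about 80%.

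The documents give no rate, effect size or power for H3b.

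**2. Inputs for H3b.** From the plan: 78 effective per arm, six tests, two-sided 0.05. Assumed: prescribed participants are positive at 95% of tests in both arms; others have a mean control positive rate of 15% or 25%, within-person correlation 0.3 or 0.5, and each person's probability is halved by M-ROCC; the prescribed share q runs from 0 to 40%. The analysis is a linear model on the count, with 1,500 simulated trials per setting.

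**3. Mechanism by hand, in one setting (15%, correlation 0.5).**

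Participants without a prescription:
- Control: mean 6 × 0.15 = 0.90; variance 6 × 0.15 × 0.85 × (1 + 5 × 0.5) = 2.68.
- M-ROCC: mean 0.45; variance 36 × 0.25 × (0.5 × 0.15 × 0.85) + 6 × [0.075 − 0.25 × (0.0225 + 0.06375)] = 0.574 + 0.321 = 0.894.
- Average variance 1.786, SD 1.34 (simulated 1.33).

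At q = 0.30, prescribed users have mean 5.70 and variance 6 × 0.95 × 0.05 = 0.285:
- Control: 0.7 × 2.68 + 0.3 × 0.285 + 0.21 × (5.70 − 0.90)² = 1.87 + 0.09 + 4.84 = 6.80.
- M-ROCC: 0.7 × 0.894 + 0.3 × 0.285 + 0.21 × (5.70 − 0.45)² = 0.63 + 0.09 + 5.79 = 6.50.
- SD = √6.65 = 2.58 (simulated 2.57). Difference = 0.7 × 0.45 = 0.315 (simulated 0.30).

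Power ≈ Φ(difference / (SD × √(2/78)) − 1.96), with √(2/78) = 0.160:
- q = 0: 0.45 / (1.34 × 0.160) = 2.10, power 56% (simulated 57%).
- q = 0.30, unadjusted: 0.315 / (2.58 × 0.160) = 0.76, power 12% (simulated 10%).
- q = 0.30, adjusted for the baseline test, which explains 69% of residual variance in the simulation: SD = 2.58 × √0.31 = 1.44; 0.315 / (1.44 × 0.160) = 1.37, power 28% (simulated 27%).

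**4. Range over the four rate and correlation settings (simulated power).**

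| Prescribed share | Unadjusted | Adjusted for baseline BZD test |
|---|---|---|
| 0% | 57-94% | 77-97% |
| 5% | 34-75% | 54-87% |
| 10% | 25-60% | 42-80% |
| 20% | 16-39% | 30-65% |
| 30% | 10-26% | 24-54% |
| 40% | 9-19% | 19-44% |

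Adjusted power exceeds unadjusted power in all 24 combinations, including with nobody prescribed.

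**5. Other assumptions.** With 5-30% prescribed and positive at 80-100% of tests, and others 15-20% positive with a 50-60% reduction, unadjusted power is about 13-66% and baseline-adjusted power about 25-89%, again higher in every setting.

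**6. Validity.** With no effect, a 20% rate and 30% prescribed (3,000 trials), the rejection rate is 0.052 unadjusted and 0.052 adjusted. Under an effect, the two estimates agree closely (for example −0.52 and −0.53 tests at a 25% rate, correlation 0.3 and 30% prescribed). Adjustment changes the precision, not the quantity estimated.

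**The case against.** **Counting prescribed use may be intended.** Objective 1.2.b speaks of benzodiazepine use without the qualifier illicit that the primary objective carries. Section 2.1 treats BZD prescribing during treatment as part of the problem, and 7.2.2 lists less need for such medication among possible benefits. This stands. A reader might infer that prescribed positives are wrongly counted; the documents do not support that. They simply do not say which use is meant.

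**The prescribed share is unknown.** A reader might take "More than 30% of patients with OUD get benzodiazepine (BZD) prescriptions during the first year of opioid treatment" as the share in this trial and conclude that prescriptions overwhelm the comparison. That figure is cumulative over a first year and comes from a cited source. It is not the share on a BZD in weeks 13-24 here. Constant positivity unaffected by the intervention is also an assumption: as-needed use and tapering would weaken it. Both points stand, so no single power figure should be quoted. The direction does not depend on them, since the baseline test helps even at 0% prescribed.

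**It is not bias.** Chance imbalance in BZD use is ordinary sampling error, already reflected in the standard error. This stands.

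**It is a secondary outcome with no power target**, one of four in a false discovery rate family. This limits the weight of the point but is no reason to leave out a covariate already collected.

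**Conclusion.** The point holds as one of precision. H3b counts every BZD positive, persistent users inflate the between-person variance, and no baseline adjustment is prespecified although the test is taken before randomization. Under the assumptions in step 5, power rises from about 13-66% to about 25-89%. Those figures rest on assumed rates, effects and prescribed shares, none of which the documents give.

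The repair is partial. Baseline adjustment removes variance but does not restore the difference diluted by participants whose result cannot change (0.45 down to 0.315 tests in the worked setting).

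Two further readings go too far. Adjusting for baseline prescription status recovers more in many of the settings, but the documents do not clearly schedule that item before randomization, so it cannot be relied on. Counting only positives in periods without a reported prescription would condition on a self-report made after randomization that the intervention may change: someone who obtains a new prescription would leave the count and look improved.

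**What to change.** In 9.6:
1. Name the model for H3b and prespecify the baseline oral fluid BZD result (positive or negative) as a covariate, whether or not the arms are imbalanced.
2. Keep the all-positives outcome and state that H3b targets any BZD use, prescribed or not.
3. If the logistic GEE is used for this outcome, say whether the reported effect is conditional on the baseline result or averaged over it, because the two odds ratios differ.
4. Label any analysis by prescription reported on the weekly survey as exploratory, with the reason: the report is made after randomization, is self-reported, and may be changed by the intervention.
5. Do not make the analysis depend on baseline prescription status.

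The cost is SAP wording. No visit or test is added, and the covariate should be nearly complete because 9.3 requires baseline assessments to be finished before randomization. The change should be dated before anyone sees BZD results by arm; Table 2 lists the data analysts and methodologists as unblinded, so the date matters.
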